We propose a prospective, randomized, double-blinded, placebo-controlled clinical trial on the use of perioperative intravenous lidocaine infusion in order to decrease pain scores and opioid consumption after robotic-assisted prostatectomy and robot assisted partial nephrectomy.

Patients undergoing urological robotic assisted surgery will be randomized 1:1 to receive either intraoperative 0.8% lidocaine or normal saline at 1 mg/kg/h for patients younger than 65 years and 0.5 mg/kg/h for patients greater than or equal to the age of 65 to be delivered by continuous infusion for 24 hours intra- and post-operatively. Opioid use will be monitored for up to 14 days post-operatively as well as pain scores.

OBJECTIVES AND SCIENTIFIC AIMS

Clinical Hypotheses:

Primary Hypothesis:

We hypothesize that use of perioperative lidocaine infusion for 24 hours in urology robotic surgeries would result in less pain and less opioid use compared to the placebo.

Exploratory Hypotheses:

We hypothesize that the use of the lidocaine infusion compared to placebo would:

1. result in less opioid consumption in first 24 hours and 14 days post-operatively
2. decrease length of stay in the PACU and improve SpO₂ levels in PACU
3. decrease postoperative nausea and vomiting
4. decrease time to first ambulation after the surgery
5. improve recovery of bowel movements after surgery
6. improve patient satisfaction levels after surgery
7. decrease length of stay in hospital

Therefore:

Primary Endpoint is:

- Difference in post-operative pain

Secondary Endpoints are:

- Difference in opioid consumption in first 24 hours, discharge and 14 days post-operatively (utilizing morphine equivalents)
- Difference in length of hospital stay determined by surgeon excluding social factors that may delay discharge (discharge readiness; hours)
- Difference in post-operative ileus duration (hours)
- Difference in time in the Post Anesthesia Care Unit (PACU) after surgery (discharge readiness and actual discharge; minutes)
- Difference in return of flatus after surgery (hours)
- Difference in time to out of bed to chair after surgery (hours)
- Difference in time to first ambulation in the hallway after surgery (hours)

BACKGROUND AND STUDY DESIGN/INTERVENTION

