In recent years, the risk of opioids in the post-operative period has gained interest due to the growing epidemic of addiction, dependence, and overdose¹. The rate of drug overdose secondary to opioids has continued to increase at an alarming rate (Figure 1)². This has been a primary point of concern in all fields of medicine and Urology has not been an exception³. This is also a nationwide government and public health concern. This has generated an increased focus on the use of non-opioid analgesics after surgery such as intravenous lidocaine⁴.

[figure not shown]

Figure 1: CDC report of age-adjusted drug overdose death rates, by opioid category: United states, 1999-2016.

Opioids remain the primary source of relief for postoperative pain and have the potential to lead to significant morbidity⁵. Opioids may delay recovery following surgery and have many well-known adverse effects including, but not limited to, nausea, vomiting and prolonged post-operative ileus^{6,7}. Furthermore, in one study, they inadequately provided pain control in 50-60% of postoperative patients. This is a frequent report of patients because of the less than optimal utilization of the medications in fear of their dose dependent adverse effects and various contraindications⁷. On the other hand, surplus medication following surgery is another prominent component of the opioid problem in Urologic practices. Bates et al. found that of the 586 patients that underwent a urological procedure that they reviewed, 67% of them had collected surplus medication¹. It is both necessary and beneficial for surgeons and patients to utilize dose-sparing strategies following surgery to decrease overall opioid usage and outpatient requirement.

One mechanism that has already been employed for overall improvement in prostatectomies and partial nephrectomies is the use of the robotic assisted approach. Robot assisted partial

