Patient may go to the floor or ICU with the infusion. Orders will be included in surgeon's post-operative orders including the stop time at 24 hours. The infusion pump will be programmed using Guardrails settings, it will be on separate infusion pump from IV fluids with sign for pump - local toxicity, obtained from anesthesia pain nurse.

Patients will be monitored clinically for toxicities during the postoperative period. Per standard of care the nurse caring for the patient will be required to document any adverse events to lidocaine every four hours and anesthesiology pain nurses will monitor these reports. If patients experience the presence of perioral paresthesia, metallic taste, tinnitus, confusion, agitation,

muscle spasms, and seizures, the lidocaine infusion will be stopped and a lidocaine toxicity protocol will start by the standard of care. The subject will be removed from the study.

At initial follow-up appointment, patient will be asked to bring in prescribed opioids, if applicable, to determine how much was required in their outpatient recovery. Pill count will be done and compared to distributed quantity. VAS score will be also assessed.

THERAPEUTIC AND DIAGNOSTIC AGENTS

Lidocaine is the intravenous analgesic. Lidocaine infusion will be stored and dispensed by the Investigational Pharmacy at University Hospital. A 0.8% Lidocaine infusion will be injected intravenously using an administration set with a filter at a constant rate of 1 mg/kg/h for ages < 65 and 0.5 mg/kg/h for ages ≥ 65. Patients with BMI ≥ 40 will be dosed using ideal body weight.

RECRUITMENT PLAN

Patients will be recruited from the practices of the Division of Urology, Department of Surgery. The study will be introduced to every eligible patient scheduled for robot assisted laparoscopic prostatectomy and robot assisted laparoscopic partial nephrectomy by the participating consenting physicians from the Department of Surgery-Urology Division and a written consent obtained prior to surgery by the consenting research personnel. Candidate subjects will be provided time to consider the study, to read the informed consent document at their convenience, and discuss the study with family and others, as desired.

PRETREATMENT EVALUATION

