Surgical complications will be assessed prospectively and retrospectively and reviewed using the institutional standard for complications reporting for all surgical patients as followed by the Department of Surgery. Standardized graded complications and adverse effects at UM utilize the five-point modified Clavien-Dindo system. Grade I include complications requiring monitoring but no intervention; Grade II requires bedside or medical treatment; Grade III constitute adverse events requiring surgical or procedural intervention with return to normal functioning; Grade IV includes disabling, life-threatening complications with resulting functional loss and grade V is death of the patient. This is a modification of the Clavien-Dindo system for reporting complications with defined, categorized and classified events that will be segregated into time periods of ≤ 30 days, 31-90 days and > 90 days after surgery and includes medication complications following NCI CTCAE version 5 guidelines.

CRITERIA FOR THERAPEUTIC RESPONSE/OUTCOME ASSESSMENT

If the surgery is aborted for any reason before attempted excision of the mass or intravenous infusion fails for any reason, the patient will be removed from the study and replaced. Based on past experience these issues are rare events. If a partial nephrectomy converts to radical nephrectomy, infusion will be continued and the data will be collected. If any robotic procedure converts to an open procedure, the subject will be excluded from the study. Lidocaine infusion will be continued or started (if subject is receiving normal saline) per surgeon request.

The intraoperative period is defined as the period from anesthesia induction to the extubation of the trachea. The surgical time is determined from the incision to the final skin closure.

The postoperative period is defined as the period from the extubation to the study endpoint at 14 days \pm 7 days.

Blood loss is defined as the estimate accounted from the suction device and absorptive sponges during the procedure, as described and agreed upon by the surgeon, anesthesiologist, circulating nurse, and surgical technician as covered by institutional guidelines.

Post-operative pain will be defined by the patient through the use of a 10 cm visual analog scale (VAS) and 11 point numeric scale (0-10).

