Length of hospital stay will be defined as the time the subject leaves the OR until subject meets standardized discharge criteria according to the surgeons' protocol, which will exclude social factors delaying real discharge times.

Post-operative ileus duration is defined as return of bowel function in hours from extubation per patients recall following nursing inquiry. Documentation will be done per standard of care by the nurse caring for study patient.

Flatus return is defined as return of flatus in hours from extubation per patients recall following nursing inquiry. Documentation will be done by nurse caring for patient following standard of care.

Patient satisfaction will be assessed 24 hours post-operative by Post Anesthesia Patient Satisfaction Assessment by research staff.

CRITERIA FOR REMOVAL FROM STUDY

Patients will be withdrawn from the study if they express a desire to do so, if it is determined to be in the patient's best interest to do so, or if they do not undergo initiation of their surgical procedure as stipulated previously. If lidocaine infusion is stopped subject will be excluded from analysis. If surgery is converted from robotic assisted to open the subject will be excluded from analysis. Patients who are not evaluable for the study primary endpoint by failure to obtain

data for the primary endpoint will be excluded from the study and further analysis will not be performed.

BIOSTATISTICS

Sample Size

The primary outcome for the study is the patient's pain score at discharge. Although additional analyses are planned, the sample size estimate is based on this outcome. Assuming a common standard deviation of two-points, a sample size of 40 with 20 per treatment arm will provide 80% power to detect a 2-point difference between groups when testing a two-sided alternative at the 5% level of significance using Wilcoxon Rank Sum Test. To take into account the loss to follow up, the drop-out inflated enrollment will be 46 subject with 23 subjects in each group assuming the same power.

Unadjusted and Adjusted Analysis

The unadjusted analysis will be designated as primary analysis and it will be performed to assess the pain level difference between the two groups. The adjusted analysis which will be designated as secondary analysis will incorporate other covariates like type of surgery in addition to the treatment assignments as covariate.

Proposed Analyses

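### Outpatient opioid use rests on a pill count alone, so discarded or given-away tablets count as taken, refills are missed, and an absent container has no stated rule

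*Combined protocol and SAP*

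**What the plan says.** The first secondary endpoint in Objectives and Scientific Aims is "Difference in opioid consumption in first 24 hours, discharge and 14 days post-operatively (utilizing morphine equivalents"), and the opening summary states "Opioid use will be monitored for up to 14 days post-operatively as well as pain scores".

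Inpatient opioid use is documented during the hospital stay. For the period after discharge, the Intervention section gives the whole method in two sentences. At the initial follow-up appointment the "patient will be asked to bring in prescribed opioids, if applicable, to determine how much was required in their outpatient recovery", and then "Pill count will be done and compared to distributed quantity".

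The documents describe no diary, no question on tablets taken, no question on disposal or sharing and no refill check. They give no rule for a patient who arrives without the container. Criteria for Removal from Study covers missing data for the primary endpoint only.

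The Background reports that, of 586 urology patients in a cited review, "67% of them had collected surplus medication". Under Criteria for Therapeutic Response/Outcome Assessment, the study endpoint is at 14 ± 7 days, so the count may cover anything from 7 to 21 days.

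**The concern.** A pill count measures consumption correctly only if every unused tablet is on the table and every dispensed tablet is in the denominator. Three things break this:

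- **Tablets discarded or given away** are absent from the count and so appear as consumption.
- **Refills** are absent from the distributed quantity, so use is understated.
- **A missing container** could be scored as an empty bottle or as missing data. The two choices give very different values for the same patient.

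The first error equals the number of tablets no longer present, so it can be largest in patients who used least. Opioid sparing is part of the primary hypothesis, and everything after discharge in the 14-day endpoint depends on this one count.

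**Working it through.** **The plan's own figures.** The plan states no effect size, SD or power for the 14-day opioid endpoint, so there is no figure on this point to reproduce. Its sample size concerns the "pain score at discharge". With a 2-point difference and SD 2, an exact t-test needs 17 per arm for 80% power. Dividing by the minimum Wilcoxon relative efficiency gives 17/0.864 = 19.7, so 20, and 20/0.9 = 22.2, so 23 with 10% dropout. Both match the plan but say nothing about opioid use.

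**What the rule does to one patient (assumed numbers).**
- 15 dispensed, 5 taken, 10 discarded. Recorded use is 15 − 0 = 15; true use is 5.
- 15 dispensed, 10 refilled, 5 remaining. Recorded use is 15 − 5 = 10; true use is 15 + 10 − 5 = 20.

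**What it does to the comparison (assumed inputs).** Suppose 15 tablets are dispensed, with true mean use 5 on placebo and 3 on lidocaine and SD 3. A share f in each arm is recorded at the full 15, because all leftovers were disposed of or because an absent container is scored as empty. Let f be unrelated to arm or to use.

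- Recorded difference = (1 − f) × 2
- Variance in an arm = (1 − f) × 9 + f(1 − f)(15 − mean)², averaged over arms
- For f = 0.1: placebo 8.1 + 0.09 × 100 = 17.1; lidocaine 8.1 + 0.09 × 144 = 21.06; average 19.08; SD 4.37; effect 1.8/4.37 = 0.41

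The only two-group time-point test the plan names is the Wilcoxon rank sum, and it is named for pain, so the loss on ranks is also relevant. The probability that a placebo value exceeds a lidocaine value is P = (1 − f)² × Φ(2/(3√2)) + f(1 − f) + f²/2, with Φ(0.471) = 0.681. The equivalent standardised effect is √2 × Φ⁻¹(P).

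| f | Difference | SD | Effect on means | P | Effect on ranks |
|---|---|---|---|---|---|
| 0 | 2.0 | 3.00 | 0.67 | 0.681 | 0.67 |
| 0.1 | 1.8 | 4.37 | 0.41 | 0.647 | 0.53 |
| 0.2 | 1.6 | 5.17 | 0.31 | 0.616 | 0.42 |
| 0.3 | 1.4 | 5.65 | 0.25 | 0.589 | 0.32 |

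**A second set of assumptions, by simulation.** With 20 tablets dispensed, mean use 10 against 6, SD 4 and 20 per arm, Wilcoxon power is about 85%, 65%, 45% and 30% for f = 0, 0.1, 0.2 and 0.3. With 30 tablets dispensed it is 84%, 64%, 45% and 28%.

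**The choice for an absent container.** In the first scenario with f = 0.2 and 20 per arm, simulated Wilcoxon power is about 24% if these patients are scored at 15 and a little over 40% if they are treated as missing. The unstated rule therefore matters in its own right.

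**The case against.** The strongest reply is that the plan never writes the subtraction as a formula and nowhere says that an absent container means the full supply was used. That is correct. Dispensed minus remaining is the natural reading of a count compared with the distributed quantity to find how much was required. It settles the matter for discarded and shared tablets. For a container left at home, missing is an equally open reading, and the Quality Assurance section does plan reports on missing data. What stands is that the plan does not say which.

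A reader might take the 67% in the Background as the share of patients who would be misclassified. It is a surplus rate, not a rate of failing to bring tablets when asked, and surplus still held can be counted.

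A reader might also infer that treating non-returners as missing would selectively remove low users. The documents do not show this. A patient who took every tablet also has nothing to bring, so high users could be lost instead.

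The trial was not sized for this endpoint. With a true effect of 0.67 and 20 per arm, a t-test has only about 54% power even with perfect measurement, so a missed difference could not be blamed on the count alone. Finally, patient recall has its own error, possibly over as long as 21 days, which is a reason not to replace the count with it.

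**Conclusion.** The point holds as a gap in measurement and in handling rules. Discarded and given-away tablets are recorded as used, refills are not captured, and the absent-container case is undefined. Under blinding the error is probably similar in both arms. Its likely effect is then added noise and a recorded difference pulled toward zero, not a false benefit.

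The size is unknown. The documents give no non-return or disposal rate, no quantity dispensed, and no mean or SD for outpatient use. The figures above show direction and scale under assumption only, and the loss on ranks is smaller than on means. They also assume that f is equal across arms and unrelated to use. They do not support the claim that a real opioid saving will be missed because of the pill count.

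Reach is limited to the post-discharge part of one secondary endpoint. Inpatient opioid use and the primary pain endpoint are untouched. This is a cheap improvement.

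**What to change.** At the existing follow-up visit, ask three things: how many tablets were taken, how many were discarded or given away, and whether any refill was obtained and of how many tablets.

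Keep the pill count as the main measure and define it in the plan:

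outpatient use = distributed + refilled − remaining − discarded or given away,

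then convert to morphine equivalents. For the two patients above this gives 15 + 0 − 0 − 10 = 5 and 15 + 10 − 5 − 0 = 20, the true values.

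State that when no container is brought, the reported number taken is used and the full quantity is never scored as consumed by default. Add a sensitivity analysis that treats these patients as missing.

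The cost is a few questions at a visit that already takes place, and some reliance on recall over a visit window of 14 ± 7 days. The count remains available as a check on the reported number whenever a container is present.

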Anesthesia will be maintained with 1 MAC sevoflurane, additional fentanyl and rocuronium will be given per anesthesia discretion. Quantity of all anesthetic and analgesic medications during the operation will be documented. Local 0.25% bupivacaine (10mL) without epinephrine injection will be used post-operatively during closure in all patients regardless of being in the study group or control group as a part of normal operational procedure. Reversal of neuromuscular blockade will be with sugammadex 2 mg/kg. When standard extubation criteria are met the subject will be extubated and transported to PACU.

Intervention

Fifteen minutes following endotracheal intubation, subjects will be intravenously infused with either 0.8% lidocaine at 1 mg/kg/h if < age 65 and 0.5 mg/kg/h if ≥ age 65 or an equal volume and rate of normal saline placebo as determined by the randomization table. The infusion will be continued for 24 hours after surgery. Masked infusion bags of 0.8% lidocaine or normal saline will be prepared by the Investigational Pharmacy at the University of Missouri Hospital according to the subject randomization table. Infusion preparation will occur in a blinded fashion to all clinical and research personal involved with the study case. To maintain blinding, the investigational pharmacist will enter "Study Medication" in the medical record.

In PACU patient will receive additional fentanyl or hydromorphone. Postoperative pain scores, vital measures, and opioid use will be documented. Once patient is able to tolerate oral intake, they will be switched to oral narcotics. Patient fentanyl consumption and 10 cm visual analog scale (VAS) will be utilized. VAS will be scored from a 0 "no pain" to a 10 "worst pain ever" and will be recorded by blinded research staff at 1, 2, 4, 6, 12, 24 hours post-operatively, postop day 2, any additional day during hospitalization, at time of discharge and 14-day follow up. The nurse that will be caring for these patients will document the time of first bowel movement, return of flatus and any adverse reactions per standard of care. Post-Anesthesia Patient Satisfaction Assessment will be performed at 24 h post-surgery.

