Various symptoms including perioral paresthesia, metallic taste, tinnitus, confusion, agitation, muscle spasms, and seizures have been described when the plasma lidocaine was higher than 5 $\mu\text{g}/\text{mL}$. While under general anesthesia, evidence of toxicity may be evident through bradycardia, increased intervals and widening QRS complex and may be increased with hypercapnia.¹⁶ However, it has been shown to be more cardio-protective, rather than cardio-toxic in prospective randomized study³⁶. The toxic levels of lidocaine are unlikely to be experienced at the levels used in our protocol. Our study is using the low end of the recommended dose and rate of 1-2 mg/kg/h. We additionally are utilizing a bolus only as a part of routine anesthesia induction, which is recommended to be 1-2 mg/kg and start the infusion 15 minutes after the endotracheal intubation.

Signs of lidocaine toxicity will be monitored per University Hospital standard of care protocol. This includes assessment and documentation by floor nursing staff, every 4 hours, of the signs and symptoms of lidocaine toxicity. The presence or lack of toxicity is reported in the medical record at these time points and pain nurse with the Department of Anesthesiology and Perioperative Medicine review this information. Management and review of medications will also be performed by the surgical and inpatient care teams per standard of care. Toxicity in our study will be evaluated clinically postoperatively by the presence of perioral paresthesia, metallic taste, tinnitus, confusion, agitation, muscle spasms, and seizures. Following standard of care, if there is concern of possible toxicity a lidocaine level may be ordered per standard of care.

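### The study's toxicity evaluation is postoperative and stopped patients leave the analysis; toxicity should be counted by arm from infusion start in everyone infused

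*Combined protocol and SAP*

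**What the plan says.** On signs, the Toxicities/Side Effects section separates the anaesthetised patient from the awake one. For the former: "While under general anesthesia, evidence of toxicity may be evident through bradycardia, increased intervals and widening QRS complex". For the study itself: "Toxicity in our study will be evaluated clinically postoperatively by the presence of perioral paresthesia, metallic taste, tinnitus, confusion, agitation, muscle spasms, and seizures". The same sentence stands under Protection of Human Subjects. The scheduled check is "assessment and documentation by floor nursing staff, every 4 hours, of the signs and symptoms of lidocaine toxicity".

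On timing, the Intervention section says: "Patients will be monitored clinically for toxicities during the postoperative period". Criteria for Therapeutic Response/Outcome Assessment starts the postoperative period at extubation. The Design section starts the infusion 15 minutes after intubation.

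On consequences, the Intervention section gives the same seven signs and ends "muscle spasms, and seizures, the lidocaine infusion will be stopped and a lidocaine toxicity protocol will start by the standard of care", followed by "The subject will be removed from the study". Criteria for Removal from Study adds that a stopped infusion means exclusion from analysis. Neither section makes an exception for safety data.

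Other provisions are wider:
- The Design section provides continuous ECG in the operating room.
- Evaluation During Treatment/Intervention extends toxicity monitoring to the whole hospital stay and stops the infusion on suspicion.
- In the Intervention section, nurses record "return of flatus and any adverse reactions per standard of care" and must "document any adverse events to lidocaine every four hours and anesthesiology pain nurses will monitor these reports".
- Complications are graded in all surgical patients and include CTCAE medication complications, and SAEs go to the IRB within 5 calendar days.

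**The concern.** The plan says how toxicity may show under anaesthesia, gives the drug under anaesthesia, and then describes a study evaluation that uses other signs at a later time. It also takes out of the analysis the patients in whom toxicity led to a stop. A toxicity count built from these rules could miss events during surgery and events that ended the infusion. At stake is what the trial can say about harm by arm. The pain comparison's sample size and the care of patients in the operating room are not in question here.

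**Working it through.** The point disputes none of the plan's figures. The one figure used below, 23 per arm, reproduces: with a 2-point difference, SD 2, two-sided 5% and 80% power, a t-test needs 17 per arm; dividing by 0.864 (the minimum relative efficiency of the Wilcoxon test) gives 19.7, so 20; with 10% dropout, 20/0.9 = 22.2, so 23.

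**1. Signs.** Toxicities/Side Effects names three ECG signs. Seven-sign lists appear in four places: Intervention, Evaluation During Treatment/Intervention, Toxicities/Side Effects, and Protection of Human Subjects. None of the three ECG signs is in any of them. The first five of the seven signs depend on a patient who can report or behave; the last two are motor signs, which rocuronium may mask. The list in Evaluation During Treatment/Intervention is worded as open, so absence from it does not prove that ECG signs are disregarded.

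**2. Time.** The documents give no operating time. Assume 2 to 4 hours from infusion start to extubation, with a window that opens at extubation.
- Infusion of 24 hours in total (Design): 2/24 = 8.3% to 4/24 = 16.7%.
- Infusion for 24 hours after surgery (Intervention): 2/26 = 7.7% to 4/28 = 14.3%.

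These are shares of infusion time, not of risk.

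**3. Stopped patients.** Suppose one of 23 lidocaine patients is stopped for toxicity. Among all infused this is 1/23 = 4.3%. If the exclusion were carried into a toxicity table, it would be 0/22. The stop rate is unknown; the chance of at least one stop among 23 is 1 − (1 − p)^23:
- p = 1%: 21%
- p = 5%: 69%
- p = 10%: 91%

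**4. What a complete table could show.** With zero events in 23, the one-sided 95% upper bound is 1 − 0.05^(1/23) = 12.2%. A full count describes the trial's experience; it cannot show safety.

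**The case against.** The strongest reply is that the section can be read as a division of methods: ECG signs during anaesthesia, clinical signs afterwards. Placing the start of evaluation at extubation joins a sentence in one section to a period definition in another. That reading is possible, and the continuous ECG fits it. What remains is that no text says ECG findings are recorded as toxicity, while the sentence on how toxicity is evaluated in this study names only the postoperative clinical signs.

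Second, the exclusion from analysis may concern pain only, since the analyses described under Biostatistics are of pain. The toxicity definition itself excludes nobody, and nurses chart the presence or absence of toxicity in the medical record. This is fair, and it makes the 0/22 figure conditional. But the exclusion is written without that limit and no other set is defined.

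Third, the hospital toxicity protocol and the institutional monitoring plan are not in the documents and may say more. This stands, and it limits confidence.

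A reader might infer that patients are unprotected during surgery. The documents do not support this, given the ECG and the stop on suspicion. Nor do they support the inference that adverse events of removed patients go unreported: complication grading covers all surgical patients, and the SAE rule makes no exception.

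**Conclusion.** The point holds as a minor one, with medium confidence. The stated rules leave the study's own toxicity count by arm incomplete in two respects: the anaesthetised part of the infusion, and patients whose infusion was stopped. The first rests on reading the postoperative wording with the plan's own period definition; the second on reading the exclusion as unrestricted.

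It would also be too strong to say that the trial will publish a misleading absence of toxicity. No safety endpoint or toxicity analysis is planned and no toxicity statement is promised, so the consequence arises only if one is made.

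**What to change.** State that the exclusions in Intervention and in Criteria for Removal from Study do not apply to safety. Tabulate toxicity and infusion stops by arm for every patient who received any study infusion, counted from infusion start and including those stopped, removed or converted to open surgery. Flag placebo patients later given lidocaine, which the plan allows on surgeon request after conversion.

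For the anaesthetised period, record any bradycardia, interval prolongation or QRS widening that the anaesthesiologist judges clinically relevant, with onset time. Compare with a pre-induction monitor reading, because Pretreatment Evaluation lists a baseline EKG for prostatectomy but not for partial nephrectomy. Do not make these signs an automatic stop trigger. Each stop can cost a randomised patient in the pain analysis, and the margin is 23 − 20 = 3 per arm unless stopped patients are replaced; the replacement rule for failed infusions does not say whether a toxicity stop counts.

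The cost is protocol wording, a few form fields and one descriptive table, with no change in sample size, stopping rules or staffing. There are two downsides. Non-specific bradycardia will be recorded in both blinded arms, and since both receive lidocaine 1.5 mg/kg at induction, early signs cannot be ascribed to the infusion alone. Recording may also prompt some stops on suspicion.

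If the sponsor declines, any toxicity statement should be limited to the period after extubation and should give the number of patients stopped in each arm.
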